Background PPI Use: Acid suppression therapy is commonly prescribed, particularly in the VA for symptomatic GERD relief. Our research team, which includes practicing clinicians and experienced GERD researchers (Drs. [name] and [name]) debated a design wherein we would require research subjects to discontinue all acid suppression therapy for the duration of the study. It is clear that based upon symptom burden and for the purposes of adherence to study procedure that this would not be feasible. Further, we were concerned that if acid related damage were occurring off of acid suppression, then such a design may not be ethical. Thus, we have adapted a much more "clinical" or "intention-to-treat" mindset to the study design. Indeed, in a clinical setting, patients are most often treated empirically. Thus, we will follow AGA guidelines⁹ and have subjects maintain acid suppression therapy during the intervention, with the exception of the 7-day period prior to impedance and manometry testing. To determine the effect of acid suppression on the hormonal milieu we will now draw blood pre and post medication discontinuation. The only potential confounder to this approach would be if the efficacy of the dietary intervention were dependent upon having a highly acid and refluxing esophageal environment. This does not seem biologically plausible, and additionally the efficacy of the dietary intervention to reduce GERD in our preliminary data was not acid dependent given that all subjects self-discontinued use of acid suppression medications. *We will perform secondary analysis in which changes in PPI use over time will be assessed. We will use the daily medication (type and dose) and diet checklist data and 24hr diet recall data to conduct secondary analyses and verify the assumptions of our primary model. Summary statistics by diet group will be calculated to determine if weight loss, PPI use, total CHO, and simple CHO are consistent with the study design. We will also use the linear mixed effects model to determine if total and simple CHO are associated with total percent time pH < 4 by replacing the indicator variables in the primary model with these continuous covariates and their interaction. A secondary analysis of changes in PPI use over time will be considered. For this analysis, we will use the daily medication checklist (type, amount and dose) to create continuous variables of the weekly dose of PPI. PPI dose will be the outcome in a linear mixed effects regression model that includes time modeled flexibly using restricted and diet group indicators. An analogous model using weight as the outcome will be estimated.*

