We recently conducted a nutrition intervention utilizing a low carbohydrate / high fat diet in 144 Caucasian and African American adults age 21-50 years with Class I obesity (BMI 30.0-39.9). At baseline, 25% of subjects reported experiencing GERD symptoms (heartburn, reflux and/or indigestion) at least once a week. Over 1/3 used a proton pump inhibitor (PPI) or histamine 2 receptor antagonist (H₂RA) at least once a week. At baseline, we found that subjects with GERD had significantly higher total sugar intakes (101.6 ± 50.3 vs 82.5 ± 40.9 grams/day, $p = 0.024$), but not higher total fat intakes. Notably, total sugar intake was a strong predictor of having GERD symptoms ($p = 0.007$). *Most unexpectedly, all GERD symptoms and medication use had resolved by completion of the 9-week low carbohydrate / high fat diet intervention.* Moreover, reduced total sugar intake was significantly associated with improved insulin sensitivity (HOMA-IR score: $r = 0.37$, $p = 0.001$), independent of weight loss.

Overarching Hypothesis: Our overarching hypothesis is that the type (not just the amount) of dietary carbohydrate intake contributes to GERD symptoms in obese persons.

Specific Hypothesis: Our preliminary findings suggest a physiological mechanism between dietary intake and GERD that may be related to type of dietary carbohydrate intake (complex vs simple carbohydrate). We hypothesize that modifying the type of dietary carbohydrate consumed - by reducing the proportion of simple carbohydrate (sugars) consumed - will reduce or resolve GERD symptoms and medication use in obese veterans with chronic GERD. We further hypothesize that the mechanistic effects of reducing simple carbohydrate intake is related to either: a) improved dietary fiber intake and/or glycemic load, and thus, reduced amount and duration of esophageal acid exposure; and/or b) improved insulin sensitivity which would positively influence the function of key gastrointestinal hormones (ie, gastrin, glucagon, GLP-1, ghrelin¹¹) that regulate gastric motility and/or lower esophageal sphincter function.

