Aim 1: *To determine effects of dietary carbohydrate consumed (amount and type) on percent time with esophageal pH < 4.0, as well as number of reflux episodes, GERD symptoms and GERD medication use, in 200 obese veterans who have chronic high frequency of GERD symptoms.* To meet this aim we will use a randomized controlled trial in which we manipulate amount of total and simple dietary carbohydrate intake for duration of 9 weeks.

Aim 2: To assess associations between GERD resolution variables and factors related to potential mechanisms by which modifying dietary carbohydrate intake could resolve/reduce GERD in obese veterans.

2a: We will investigate associations related to whether the effect is nutritionally mediated by measuring change in dietary fiber load and dietary glycemic load, and thus, whether these changes are related to improved gastric acid secretion (% time pH < 4), gastric motility, and/or the other parameters that comprise the Johnson-DeMeester score.

2b: We will also investigate whether effects are associated with changes in the hormonal milieu by measuring hormonal response of gastrin, glucagon, GLP-1, ghrelin and insulin, which could potentially influence gastric acid secretion, gastric motility and/or lower esophageal sphincter function.

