- **Medication Use:** will be assessed by two methods: a) we will provide subjects with a notebook that includes daily logs for them to record medication type and amount; and b) weekly interview by study nurse. In addition, we now have bloodwork being drawn pre and post weeks 1 and 9 that will inform medication use by measurement of hormone levels, i.e., gastrin.
- **24-Hour Impedance Monitoring:** will be performed by using a combined MII-pH monitoring device (Sandhill Scientific Inc; Highlands Ranch, CO) comprising a data recorder (Sleuth System; Sandhill Scientific Inc) and a 2.1 mm diameter polyvinyl catheter embedded by one pH and 6 impedance sensors at predefined positions. The pH sensors are calibrated before placement using standardized buffer solutions at pH 4.0 and 7.0 per manufacturer. The catheter is placed intranasally so that the esophageal pH sensor is positioned 5-cm above the manometrically defined upper border of the lower esophageal sphincter (LES). Intraluminal impedance is measured at 3, 5, 7, 9, 15 and 17cm above the LES. Data sampling frequency for both impedance and pH sensors is 50 Hz. Data are downloaded from the recorder and analyzed using BioView Analysis software (Sandhill Scientific Inc). Reflux episodes are identified by computerized detection (Autoscan; Sandhill Scientific Inc.) of proximally directed decreases in impedance. Tracings are also manually reviewed by an experienced investigator ([name]) to confirm accuracy and correct errors. Total, upright and supine reflux events are recorded. Acid reflux events are defined as those with pH \leq 4 and non- or weakly acid reflux events are those occurring at pH $>$ 4.

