analysis of only the complete cases would bias the results. *We will now request to subjects that inform of us they are dropping out between weeks 7 to 9 that they come in for a final visit. We have found that about 2/3 of subjects will agree to come in for a final visit even if they are not continuing to the end of study (week 9). This will significantly reduce the potential for missing data.* We will also attempt to obtain the specific reason for dropout on a case by case basis. Indirect information about the nonrandom dropouts will be obtained by using binary logistic models to predict the probability of dropping out using baseline variables. Thus, the impact of dropout on our results will be compared using assumptions that vary from missing completely at random to informative missing.

Sensitivity Analyses: We will use the daily diet data and daily medication checklist (type and amount) to conduct secondary analyses and verify the assumptions of our primary model. Summary statistics by diet group will be calculated to determine if weight loss, PPI use, total CHO, and simple CHO are consistent with the study design. We will also use the linear mixed effects model to determine if total and simple CHO are associated with total percent time < pH 4 by replacing the indicator variables in the primary model with these continuous covariates and their interaction. A secondary analysis of changes in PPI use over time will be considered. For this analysis, we will use the diary card data to create continuous variables of the weekly dose of PPI. PPI dose will be the outcome in a linear mixed effects regression model that includes time modeled flexibly using restricted and diet group indicators. An analogous model using weight as the outcome will be estimated. Our study is designed for subjects to maintain weight, but if weight loss differs by treatment arm, it may introduce confounding into our study. We will include weight loss as a covariate in our regression model to determine if our results are altered compared to the main analysis. This additional sensitivity analyses will be conducted as needed, for example where weight change is significantly different among groups, to assure effects are due to dietary not body weight change.

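### The planned medication analyses cover PPI use only, although Aim 1 concerns all GERD medication use, so a switch to an H2RA or antacid would count as a reduction

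*Combined protocol and SAP*

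**What the plan says.** Section 2.3 states Aim 1 as the effect of dietary carbohydrate on esophageal acid exposure, "as well as number of reflux episodes, GERD symptoms and GERD medication use". The specific hypothesis in the same section is that cutting simple carbohydrate "will reduce or resolve GERD symptoms and medication use in obese veterans with chronic GERD". Neither is limited to one drug class. The pilot study behind the trial also counted more than PPIs: "Over 1/3 used a proton pump inhibitor (PPI) or histamine 2 receptor antagonist" at least weekly at baseline.

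The analysis plan is narrower. Section 10.0, under Sensitivity Analyses, says "A secondary analysis of changes in PPI use over time will be considered", and for that analysis "we will use the diary card data to create continuous variables of the weekly dose of PPI". Section 2.1, under Background PPI Use, gives the same model: "PPI dose will be the outcome in a linear mixed effects regression model". Both sections also plan a descriptive check, by diet group, that PPI use, weight and carbohydrate intake match the design. No H2RA, antacid or combined outcome is specified, and no rule deals with substitution.

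The data collection is wider than the analysis. Section 6.0 provides "daily logs for them to record medication type and amount", backed by a weekly nurse interview. It also sets separate pre-test stop times for PPIs, H2RAs and antacids, so all three classes are foreseen in this population.

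**The concern.** A PPI-only outcome does not measure what Aim 1 asks. It cannot separate a subject who needs no acid drug from one who has moved to a different acid drug, because PPI dose falls to zero in both. It also misses improvement in any subject whose reflux is managed without a PPI. Such subjects can enter: Section 4.0 requires a recorded GERD diagnosis confirmed by pH testing, not PPI use, and Section 5.0 looks for patients on GERD prescriptions generally.

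At stake is any statement that a diet reduced or resolved medication use. The pilot's report that medication use resolved in every GERD subject is a main motive for the trial, and the trial would be expected to confirm or refute it. With PPI dose alone it could report a drug-sparing effect when total use of acid drugs had not changed, or miss a real one in subjects not taking PPIs.

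**Working it through.** The plan states no figure for the medication outcome (no SD, effect size or power), so there is nothing to reproduce. The check is mainly a comparison of texts.

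**Scope, side by side**

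- Aim 1 and the hypothesis (Section 2.3): GERD medication use, no class named.
- Pilot definition (Section 2.3): PPI or H2RA.
- Model outcome (Sections 2.1 and 10.0): weekly PPI dose.
- Descriptive summary (Sections 2.1 and 10.0): PPI use.
- Data recorded (Section 6.0): type and amount of medication.

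The two analyses are narrower than the aim, the pilot definition and the data.

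**How the planned outcome treats typical changes**

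- PPI stopped, nothing taken instead: PPI dose falls to zero. Correct.
- PPI stopped, H2RA or antacid taken instead: PPI dose falls to zero. This looks the same as the first case.
- H2RA or antacid only at entry, then stopped: zero throughout. The improvement is not seen.
- H2RA or antacid only at entry, then a PPI started: dose rises from zero. The worsening is captured.

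**Illustration of size (assumptions, not document figures)**

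Assume one PPI dose a day at baseline, so 7 dose-days a week, and let a share s of an arm switch completely to another acid drug taken equally often.

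- Change in mean weekly PPI use = −7 × s.
- Change in mean days on any acid drug = −7s + 7s = 0.
- s = 0.10: −7 × 0.10 = −0.7 dose-days.
- s = 0.20: −7 × 0.20 = −1.4 dose-days.

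The spurious difference between two diets with switching shares s₁ and s₂ is −7 × (s₁ − s₂). If both are 0.10 it is −7 × 0 = 0; if one is 0.10 and the other 0, it is −0.7. These results only restate the assumed shares. The documents give no switching rate and no SD for PPI dose, so it cannot be said whether such a difference would be detectable.

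**Stop periods**

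Section 6.0 stops PPIs for one week before the tests on days 7 and 63, and H2RAs and antacids for two days. A compliant subject therefore has no PPI use in those weeks because of the protocol, while the other two classes are not stopped on about 7 − 2 = 5 of the days. Any medication outcome has to set these periods aside.

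**The case against.** The strongest reply is that the PPI model was never meant as the Aim 1 medication endpoint. It sits under Background PPI Use and Sensitivity Analyses, in paragraphs that aim to check the assumptions of the primary model. The design keeps subjects on acid suppression between tests, so PPI dose can be read as a check on background therapy. That is a fair reading, but it does not remove the gap: on it, the medication part of Aim 1 has no committed analysis at all. Both sections do say in general terms that medication type will feed secondary analyses, but the only model they then specify is for PPI dose.

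Other parts of the reply stand and limit the point:

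- A reader might infer that a switcher is scored as a treatment success. The documents define no medication responder or success rule; the switch enters as a lower continuous dose.
- A reader might infer from the unequal stop times that the protocol makes lasting switching likely, or more likely in one arm. The first stop period precedes randomization, both are the same in every arm, and nothing says that subjects substitute or continue to do so afterwards.
- A reader might infer that knowing the diet drives differential switching. Diets are taught openly, but all four arms receive meal plans and dietitian instruction, and nothing says that subjects are told which diet is expected to help reflux.
- A count of days on any drug treats an antacid tablet and a PPI dose alike, and shows no change when a daily dose is lowered. It should therefore supplement PPI dose and not replace it.

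**Conclusion.** The concern holds as a mismatch of scope. Followed as written, the plan counts a change from a PPI to an H2RA or antacid as a reduction, and does not see a fall in H2RA or antacid use among subjects not on a PPI. This follows from the text and needs no assumption about rates.

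The practical size is unknown. The 0.7 and 1.4 dose-days a week rest on a daily PPI at baseline, complete switching by 10% or 20% of an arm, and equally frequent use of the substitute. A comparison between diets is biased only if switching differs by diet; equal switching produces a shared change over time. How many subjects will enter without a PPI is not given either.

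It would be wrong to conclude that the trial's main result is at risk. The primary outcome, percent time with pH below 4, is measured after all three classes have been stopped, so switching does not alter how it is scored. This is a worthwhile, low-cost improvement to a secondary outcome named in Aim 1.

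**What to change.** Before the data are examined, commit in Section 10.0 to an Aim 1 medication analysis:

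- Outcome: days per week with any acid suppressant or antacid (PPI, H2RA or antacid), reported overall and by class, from the daily log and weekly nurse interview.
- Exclude the protocol-required stop periods before both tests. The baseline value then has to come from before the first stop period.
- Keep weekly PPI dose as a companion outcome, so that dose reductions with continued daily use remain visible.
- State that medication use has resolved only when all recorded classes are zero.

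The cost is a revision of analysis wording and a little more data derivation. No new data, visits or changes to treatment are needed. The small downside is that a count of days is less sensitive to dose, which is why weekly PPI dose is retained.

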- HTLS Diet: 55% total CHO (85% complex / 15% simple CHO), 30% fat, 15% protein
- LTHS Diet: 35% total CHO (½ complex / ½ simple CHO), 50% fat, 15% protein
- LTLS Diet: 35% total CHO (85% complex / 15% simple CHO), 50% fat, 15% protein

Power Analysis and Sample Size: Our primary outcome is a continuous variable, percent time pH < 4.0 in the 24hr period. This is based on the clinical gold standard of pH < 4.0 for > 5.5% of the 24hr period. To determine sample size, we used data from 205 obese patients with chronic GERD from [name] clinic population. In this sample, the SD for percent time < pH was 9.8 and the interclass correlation was 0.39 ($\omega = \omega^2_b / (\omega^2_b + \omega^2_e)$). We used these values as inputs into a statistical simulation (10,000 replications) to determine the probability of detecting any treatment group effect using the linear mixed effects model. The following table presents the power of an overall (4 d.f.) test to detect various absolute changes in pH by diet groups ($\omega_1, \omega_2, \omega_3, \omega_4$). We assume $n_1=40$ subjects per group complete the entire study and $n_2=5$ or $n_2=3$ subjects per group complete 80% of the study before returning for pH testing. We use a two-sided significance level of 0.05.

Absolute effect size	3.7%, 3.7%, 3.7%, 3.7%	0%, 4.5%, 4.5%, 4.5%	0%, 4%, 4%, 4%	0%, 0%, 5%, 5%	0%, 0%, 0%, 7%
Power ($n_1=40, n_2=5$)	0.80	0.89	0.80	0.85	0.87
Power ($n_1=40, n_2=3$)	0.79	0.88	0.79	0.83	0.86

Power for different effect size scenarios that give 80%-90% power are presented in the table. If the absolute change in percent time pH < 4 for each of the four diet groups is 3.7%, we will have 80% power to detect any effect of diet. If 1 diet group is not effective and the other groups have a 4.5% effect, we have almost 90% power to detect a diet effect. In our pilot data, the 25th/50th/75th percentiles of percent time pH < 4 were 4.8%/8.5%/12.4%. Thus, a 3.7% decrease is a change from the median to 25th percentile, a 4% decrease is a change from the 75th percentile to the median, a 5% decrease is a change from the 80th percentile to the median, and a 7.6% decrease is a change from the 75th to the 25th percentile. The standard error for any pairwise comparison between groups will be 1.9% under all scenarios ($n_1=40$ and $n_2=3$ or $n_2=5$).

2.3 SPECIFIC AIMS:

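### The stated 1.9% standard error for a pairwise diet comparison and the printed power table cannot come from the same inputs; the variance that reproduces the table gives 2.5%

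*Combined protocol and SAP*

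**What the plan says.** Section 2.2 bases the sample size on 205 obese patients with chronic GERD, in whom "the SD for percent time < pH was 9.8 and the interclass correlation was 0.39". It does not say whether 9.8 is the total or the residual SD. These values feed a simulation of 10,000 replications, described as follows: "The following table presents the power of an overall (4 d.f.) test to detect various absolute changes in pH by diet groups". The design has 40 completers per arm, plus 5 or 3 per arm who leave at 80% of the study and return for testing. The two-sided level is 0.05.

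The printed power is 0.80, 0.89, 0.80, 0.85 and 0.87 with five early leavers per arm, and 0.79, 0.88, 0.79, 0.83 and 0.86 with three. The paragraph ends: "The standard error for any pairwise comparison between groups will be 1.9% under all scenarios", naming both early-leaver counts.

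Section 10.0 gives the model: one common baseline mean, a random subject intercept, independent errors and four diet effects multiplied by time. Time is 0 at baseline, 1 for completers and the completed proportion for early leavers.

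**The concern.** The power table and the pairwise SE are both functions of the same variance components, sample sizes and model, so one set of inputs must give both. A pairwise SE of 1.9 looks too small beside power of 0.80 to 0.89 for effects of this size.

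The 4-d.f. test asks whether any arm changes from baseline. Its first scenario, 3.7 points in every arm, contains no difference between diets and is still credited with 80% power. The table therefore does not directly describe contrasts between diets, and the 1.9% sentence is the only precision stated for them. Section 2.2 names a control diet, and section 10.0 says the study will address whether simple or total carbohydrate drives reflux, so a reader will rely on that figure.

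**Working it through.** **Inputs.** From section 2.2: SD 9.8, ρ = 0.39, 40 completers per arm with t = 1, n₂ = 5 or 3 early leavers per arm with t = 0.8, 4 d.f., α = 0.05. From section 10.0: the model.

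**Formulas.** Let σ² be the total variance of one measurement. Per arm, S₁ = Σt = 40 + 0.8n₂ and S₂ = Σt² = 40 + 0.64n₂. Over four arms, N = 4(40 + n₂). Define

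- A = S₂/(1 − ρ²)
- k = S₁²/[2N(1 + ρ)]

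The information matrix for the four diet effects, after eliminating the common baseline mean, is (A·I − k·J)/σ², where I is the identity and J the all-ones matrix. Then

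- SE of a pairwise difference = σ√(2/A)
- SE of one arm's change = σ√{1/A + k/[A(A − 4k)]}
- noncentrality λ = [A·Σβ² − k(Σβ)²]/σ², and power = P(χ²₄(λ) > 9.49)

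For n₂ = 5: S₁ = 44, S₂ = 43.2, N = 180, A = 43.2/0.8479 = 50.95, k = 1936/500.4 = 3.869.
For n₂ = 3: S₁ = 42.4, S₂ = 41.92, N = 172, A = 49.44, k = 3.760.

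**Reproducing the table: 9.8 as residual SD.** σ = 9.8/√0.61 = 12.55, so σ² = 157.4. For the first scenario with n₂ = 5, λ = (50.95 × 54.76 − 3.869 × 219.04)/157.4 = 12.34, which gives power 0.815. All cells:

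| Scenario | Printed (n₂=5) | Residual SD 9.8 | Total SD 9.8 | Printed (n₂=3) | Residual SD 9.8 | Total SD 9.8 |
|---|---|---|---|---|---|---|
| 3.7, 3.7, 3.7, 3.7 | 0.80 | 0.815 | 0.966 | 0.79 | 0.801 | 0.961 |
| 0, 4.5, 4.5, 4.5 | 0.89 | 0.895 | 0.989 | 0.88 | 0.885 | 0.987 |
| 0, 4, 4, 4 | 0.80 | 0.802 | 0.961 | 0.79 | 0.788 | 0.955 |
| 0, 0, 5, 5 | 0.85 | 0.859 | 0.980 | 0.83 | 0.847 | 0.977 |
| 0, 0, 0, 7 | 0.87 | 0.883 | 0.986 | 0.86 | 0.872 | 0.984 |

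The residual reading matches every cell within 2 points. The total-SD reading exceeds every cell by about 10 to 17 points. With 10,000 replications the Monte Carlo error at power 0.80 is √(0.8 × 0.2/10,000) = 0.004, so noise cannot explain that gap. A 3-d.f. test of equality between diets would give 0.05 in the first scenario, which confirms that the table describes the 4-d.f. test.

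**Standard errors.**

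| Reading of 9.8 | Pairwise SE (n₂=5 / 3) | One-arm SE (n₂=5 / 3) |
|---|---|---|
| Residual SD (σ = 12.55) | 2.49 / 2.52 | 1.85 / 1.88 |
| Total SD (σ = 9.8) | 1.94 / 1.97 | 1.45 / 1.47 |

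For example, 12.55 × √(2/50.95) = 2.49 and 9.8 × √(2/50.95) = 1.94.

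**Checks.** A simulation with estimated variance components (4,000 replications per cell) under the residual reading gave power 0.789 to 0.885, an SD of pairwise estimates of 2.46 to 2.56 and an SD of one-arm estimates of 1.84 to 1.90. Fitting the residual SD freely to the table at ρ = 0.39 gives 9.9, with pairwise SE 2.51 to 2.55. Setting the pairwise SE to 1.9 gives power of 0.97 to 0.99 in every scenario.

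**What the difference means for one contrast.**

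| Quantity | SE 1.9 | SE 2.5 |
|---|---|---|
| 95% half-width (1.96 × SE) | 3.7 | 4.9 |
| Difference detectable with 80% power (2.80 × SE) | 5.3 | 7.0 |
| Power for a 4-point difference | 0.56 | 0.36 |
| Power for a 5-point difference | 0.75 | 0.52 |

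**The case against.** The strongest reply is that the SE may be right and the table wrong. An SD described for a clinic sample normally means the total SD. On that reading the pairwise SE is close to 1.9, and overall power is higher than claimed, so the error is conservative. The quoted pilot quartiles (4.8, 8.5, 12.4) span 7.6 points: a total SD of 9.8 already implies marked skew, and 12.55 would imply more. That evidence is only suggestive, because the pilot data may not be the 205-patient sample. A simple baseline-adjusted comparison with 45 per arm and total SD 9.8 also gives 9.8 × √0.8479 × √(2/45) = 1.90, although with 43 per arm it gives 1.95.

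This stands as a reason not to declare 2.5% correct. It does not remove the conflict, because the same reading puts the table 10 to 17 points too low.

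Two further points are fair. No pairwise contrast or decision rule is tied to the 1.9%, and the sample size rests on the overall test. Section 10.0 also allows disease-severity covariates, which could reduce the realised SE by an amount the protocol does not give. Neither reconciles two planning figures printed together.

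**Conclusion.** The concern holds: on either reading of 9.8, a printed planning figure is wrong. If 9.8 is the residual SD, the table stands and the pairwise SE is 2.5, about 31% above the stated 1.9. If it is the total SD, the SE is approximately right (1.94, or 1.97 with three early leavers) and the table should show about 0.96 to 0.99.

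The documents do not settle which applies. The residual reading reproduces all ten cells. It also offers a likely explanation for the sentence: the one-arm SEs, 1.85 and 1.88, both round to 1.9 as the sentence requires, whereas 1.97 rounds to 2.0. That a within-arm SE was labelled as pairwise is an inference. The inconsistency itself is certain, given the section 10.0 model, ρ = 0.39 and the stated numbers per arm. It affects the stated precision and power, not the validity of the primary test or the conduct of the trial.

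**What to change.** In section 2.2, state whether 9.8 is the total or the residual SD and give both variance components. Then correct the figure that does not follow:

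- If residual: restate the pairwise SE as 2.5% and label 1.9% as the SE of one arm's change from baseline.
- If total: keep the pairwise SE at about 1.9 to 2.0% and recompute the power table.

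In either case add the minimum detectable pairwise difference at 80% power: about 7.0 points with an SE of 2.5, or 2.80 × 1.94 to 1.97 = 5.4 to 5.5 points under the total-SD reading.

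The cost is one definition and one or two restated figures. The stated pairwise precision may become less favourable. No sample size, visit or analysis step has to change because of this correction alone.
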